0.001-0.01), benign (B, pathogenic possibility < 0.001). The results of gene detection in this study only classified pathogenic and possible pathogenic mutations as positive mutations, and homozygotes and compound heterozygotes of autosomal recessive inheritance, single heterozygotes and homozygotes of autosomal dominant inheritance, and hemizygotes of X-linked inheritance were classified as disease positive. The unclear clinical significance is not directly used as the basis for clinical diagnosis. It is necessary to combine the clinical, if necessary, to carry out the corresponding family member verification, auxiliary examination, clinical follow-up.

(3) MS / MS data collection and standardization : The collected data include (1) laboratory background information including instrument type, reagent type, quality control material type, laboratory quality control rules, filter paper type, normal population range ; (2) Quality control data included quality control number, quality control type, quality control batch number, amino acid internal standard batch number, acylcarnitine internal standard batch number, factory time, experimental time, and test value of each quality control analyte ; (3) Screening test data include screening number, gestational age, breastfeeding method, native place (province, city), newborn gender, birth date, birth weight, sample number, blood collection time, etc. ; (4) The data of confirmed cases included screening number, confirmed disease, blood ammonia test, blood gas analysis, blood routine, liver function test, urine GC-MS test, imaging examination, gene detection information and other tests. The fluctuation range of the detection concentration of the corresponding batch of quality control samples was within the target value ± 3 s. Finally, the data were collected and sorted into the negative database and the positive database. In order to eliminate the influence of regional differences, the series detection index data were standardized.

(4) By analyzing the correlation between large sample gene data and tandem mass spectrometry data and the correction of clinical prognosis, a neonatal genetic disease gene screening database and an artificial intelligence risk assessment

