3.6 Observation items

(1) Positive detection rate of common genetic diseases in neonates : the results of genetic testing of enrolled neonates showed that the proportion of homozygous and compound heterozygotes of autosomal recessive inheritance, single heterozygote and homozygous of autosomal dominant inheritance, and hemizygote of X-linked inheritance accounted for the total number of people tested.

(2) The corresponding pathogenic genes and pathogenic variation carrying rate of common neonatal genetic diseases : that is, the proportion of the total number of occurrences of pathogenic variation, suspected pathogenic variation and

unknown clinical significance variation in the genetic test results of the enrolled neonates according to the ' ACMG genetic variation classification criteria and guidelines ' and ' genetic variation classification criteria and guidelines (2017) '.

- (3) The carrying rate of high-frequency mutation sites in the population : that is, the mutation sites with a population carrying rate greater than 1 %.
- (4) Establish a complete protein structure and catalytic activity analysis process, and develop artificial intelligence protein analysis tools for pathogenicity prediction of mutation sites.
- (5) Preliminary identification of the pathogenicity of high-frequency VUS mutation sites : The protein structure and enzyme catalytic activity characteristics of high-frequency VUS mutation sites were predicted by artificial intelligence tools, and the metabolic spectrum differences between positive, carrier and negative samples of high-frequency VUS mutation sites were clarified by combining with tandem mass spectrometry metabolite data, which provided a basis for the pathogenicity judgment of VUS mutation.
- (6) Gene-metabolism correlation : machine learning algorithms such as random forest, support vector machine, elastic network and multi-layer perceptron are used to construct prediction models of common genetic diseases, so as to realize accurate diagnosis of common genetic diseases through tandem mass spectrometry metabolomics data, and expand 2-3 diseases that can be diagnosed by tandem mass spectrometry.

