3.7 Statistical processing

IBM-SPSS 26.0 statistical software and R language (Version 4.1.0) were used for statistical analysis of the test results, and the positive rate of neonatal genetic disease screening (common positive disease cases, common positive sites) was counted. The carrying rate of common mutation sites in newborns was counted. The measurement data were expressed as mean \pm standard deviation ($x \pm s$), and t test was used for comparison between groups. The count variables were expressed as values or rates (%), and the comparison between groups was tested. Unconditional logistic regression analysis was used to evaluate the correlation between genotype and

clinical phenotype. Generalized multifactor dimensionality reduction (GMDR) was used to analyze gene-gene interaction and genotype-phenotype correlation. Based on tandem mass spectrometry data, machine learning algorithms such as random forest, support vector machine, elastic network, and multi-layer perceptron were used to construct genotype prediction models. Accuracy, Balanced accuracy, sensitivity, and specificity were used to evaluate the prediction effect of the model.

4. Ethics in clinical research

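### At any X-linked high-frequency VUS site, a zygosity-based positive-versus-carrier comparison is boys versus girls, and the planned unadjusted t test cannot separate the variant from sex

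*Combined protocol and SAP*

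**What the plan says.** Section 3.3(2) sets the rule for a positive result. It is written for the two highest variant grades, since the study "only classified pathogenic and possible pathogenic mutations as positive mutations". For X-linked inheritance it lists one genotype: "hemizygotes of X-linked inheritance were classified as disease positive". Homozygotes are named for the autosomal modes but not for the X-linked mode. Section 3.6(1) repeats the zygosity rule for the detection rate, ending with "hemizygote of X-linked inheritance accounted for the total number of people tested", and there names no variant grade.

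Section 3.6(3) calls a site high-frequency above 1% carriage. At the high-frequency VUS sites, section 3.6(5) plans that "the metabolic spectrum differences between positive, carrier and negative samples of high-frequency VUS mutation sites were clarified", combined with a predicted protein structure and enzyme activity, "which provided a basis for the pathogenicity judgment of VUS mutation". Neither positive nor carrier is defined there for a VUS.

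For continuous data section 3.7 says that "t test was used for comparison between groups". It names no covariate, matching or stratification. The standardization of the MS/MS values in 3.3(3) is aimed at regional differences. Sex is among the items collected ("newborn gender, birth date, birth weight"), but no analytic use of it is stated.

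**The concern.** Rare karyotypes aside, a boy has one X chromosome and cannot be heterozygous at an X-linked site, and a girl cannot be hemizygous. If the status groups in 3.6(5) are formed by zygosity, status and sex become the same variable in the positive-versus-carrier comparison. Any ordinary sex difference in an amino acid or acylcarnitine then appears as a metabolic effect of the variant. Sex can also exaggerate, hide or reverse a real effect.

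At stake is the metabolite evidence that the plan uses when it judges a VUS. Autosomal sites do not have this problem, because there zygosity does not depend on sex.

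**Working it through.** The documents give no significance level, effect size or sample-size derivation for this comparison, so there is no planned figure to reproduce.

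**Inputs from the documents.** N = 40,000 newborns; the 1% carriage threshold (3.6(3)); 11 + 28 = 39 analytes.

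**Assumptions.** Half the newborns are boys; Hardy-Weinberg proportions in girls; two-sided 5% tests; the VUS has no metabolic effect; an analyte differs between the sexes by d = 0.05, 0.1, 0.2 or 0.3 SD. The documents give no value for d.

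**Step 1: group sizes at a 1% X-linked site.** With allele frequency q, carriage is c = 0.5q + 0.5(2q − q²). Setting c = 0.01 gives q = 0.00668.
- Hemizygous boys: 20,000 × q ≈ 134.
- Heterozygous girls: 20,000 × 2q(1 − q) ≈ 265.
- Homozygous girls: 20,000 × q² ≈ 0.9.
- Non-carriers: about 39,600, of whom 50.2% are boys.

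The positives are all boys under the rule as written. They would still be 99.3% boys if homozygous girls were counted as positive. With 54% boys instead of 50%, the counts are 148 boys and 251 girls, so the picture is the same.

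**Step 2: bias when the VUS does nothing.**
- Positive versus carrier: d.
- Positive versus negative: d × (1 − 0.502) ≈ +d/2.
- Carrier versus negative: −d × 0.502 ≈ −d/2.

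These biases are essentially unaffected by the number of carriers; only the chance of a significant result rises with it.

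**Step 3: rejection rates.** The standard error in SD units is √(1/n₁ + 1/n₂): 0.106 for positive versus carrier, 0.0867 for positive versus negative and 0.0616 for carrier versus negative. The rejection rate is Φ(|bias|/SE − z) + Φ(−|bias|/SE − z), with z = 1.96 at 5% and z = 3.22 at 0.05/39.

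| d (SD) | Positive vs carrier, 5% | Positive vs carrier, 0.05/39 | Positive vs negative, 5% | Carrier vs negative, 5% |
|---|---|---|---|---|
| 0.05 | 7.6% | 0.3% | 6.0% | 6.9% |
| 0.1 | 15.6% | 1.1% | 8.9% | 12.9% |
| 0.2 | 47% | 9.1% | 21% | 37% |
| 0.3 | 81% | 35% | 41% | 69% |

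As a check, 4,000 simulated t tests of positive versus carrier gave 15.1%, 46.1% and 81.4% at 0.1, 0.2 and 0.3 SD.

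**Step 4: can adjustment for sex help?** Not for positive versus carrier. With columns for intercept, positive status and male sex, the design matrix has rank 2 rather than 3, so the two effects cannot be estimated separately. Against negatives it can: simulated hemizygous boys versus variant-negative boys rejected in about 5% of runs at every d from 0 to 0.3 SD.

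**The case against.** Five points can be made on the other side.

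- **The rule is not written for a VUS.** Section 3.3(2) limits positives to the two highest grades and treats uncertain significance separately. This stands: carrying the rule over is an inference, and the gap in the text is that the groups are undefined. But no other zygosity rule is given, 3.6(1) restates it without a grade, and any similar grouping gives nearly the same sex split.
- **There may be no such site.** No X-linked VUS above 1% is identified. This stands and limits the reach of the point. The plan does, however, provide for X-linked inheritance and does not exclude it from 3.6(5).
- **The sex difference is assumed.** This also stands. The inflation is slight at 0.05 SD, and Bonferroni would reduce it greatly at 1% carriage, although 3.7 states no multiplicity correction. The aliasing itself does not depend on d.
- **The metabolites are not the whole verdict.** A reader might infer that a harmless X-linked VUS would be declared pathogenic on one t test. The documents do not support that. Objective (3) directs the metabolite analysis to sites with low enzyme activity, 3.6(5) combines it with the protein prediction and calls the identification preliminary, and 3.3(2) does not let a VUS directly support a clinical diagnosis.
- **The three-group pattern may expose the artefact.** A pure sex effect moves positives and carriers in opposite directions from the negatives, which is not the graded pattern expected of a damaging variant. A careful analyst might notice. The plan does not ask for this check, and the pattern would be blurred where a real effect is also present.

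**Conclusion.** The point holds conditionally. If the groups in 3.6(5) are formed by zygosity, then at any X-linked VUS above 1% carriage the positive-versus-carrier contrast is fully aliased with sex, and neither the planned t test nor a sex covariate can repair it. Each group against mixed-sex negatives carries about half of any sex difference.

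At the plan's own threshold, and for assumed sex differences of 0.05 to 0.3 SD, false positive-versus-carrier findings run from about 8% to 81% at a nominal 5%, or from 0.3% to 35% after Bonferroni over 39 analytes. Positive versus negative runs from 6% to 41% at a nominal 5%. These rates rest on assumed sex differences, an equal sex ratio and Hardy-Weinberg proportions. How many sites are affected is unknown and could be none.

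The consequence is distorted metabolite evidence at those sites, not a wrong classification by itself. The change is worth making because it costs almost nothing.

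**What to change.** In 3.6(5) and 3.7, state that for X-linked genes hemizygous boys are compared with variant-negative boys and heterozygous girls with variant-negative girls, and that positive versus carrier is not interpreted for these genes. The same text should define positive and carrier at a VUS site and say where homozygous girls belong, since the present X-linked rule gives them no category.

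No new data are needed, because sex is already collected. The reference group falls from about 39,600 to about 20,000 per sex, but the small variant group sets the precision. For 134 boys the standard error moves from 0.0867 to 0.0868 SD, and for 265 girls from 0.0616 to 0.0618 SD. What is given up is the direct positive-versus-carrier contrast at X-linked sites, which could not be interpreted anyway.

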research object	Gene screening data of 40,000 newborns (138 genes related to 133 common genetic diseases) and tandem mass spectrometry data (11 amino acids and 28 acylcarnitines).
Inclusion criteria	(1) Newborns who underwent genetic screening and tandem mass spectrometry at the same time. (2) Age : 0-28 days, gestational age 37-42 weeks.
Excluded criteria	Data that meets any of the following conditions need to be eliminated : (1) Neonatal data with unclear clinical basic information ; (2) Lack of traceability core information data ; (3) The data that the test results cannot be analyzed and interpreted.
sample size	Gene screening and tandem mass spectrometry data of 40,000 newborns.
data collection	(1) Basic information : gender, age, sample type, subject traceability number / ID number, etc. (2) Clinical symptoms, biochemical and imaging data of positive samples. (3) Gene detection results and tandem mass spectrometry results.

	(4) Date of test data, instrument model, reagent type, etc.
Statistical processing	IBM-SPSS 26.0 statistical software was used to analyze the test results. Logistic regression analysis was used to evaluate the correlation between genotype and clinical phenotype. Generalized multifactor dimensionality reduction method was used to analyze gene-gene interaction and genotype-phenotype correlation. Based on tandem mass spectrometry data, machine learning algorithms such as random forest, support vector machine, elastic network, and multi-layer perceptron were used to construct a genotype prediction model. The prediction effect of the model was evaluated by accuracy, balance accuracy, sensitivity, and specificity.
abbreviation	Principal Investigator, PI; tandem mass spectrometry, MS/MS; Inborn errors of metabolism, IEM

1. project basis

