1.2 Creativity

This study is a multi-center cooperative study of the South China Neonatal Genetic Screening Alliance. Through the analysis of 40,000 cases of neonatal genetic screening data and MS / MS data, the incidence of common genetic diseases in newborns in China and the carrying rate of related gene pathogenic mutations are deeply understood, and the types of diseases, gene selection, gene screening process, interpretation of gene screening results, follow-up and treatment of screening positive patients and other related contents of neonatal genetic screening are preliminarily clarified, so as to provide scientific research basis for the feasibility, clinical value and social benefits of large-scale genetic screening.

In addition, this study will clarify the correlation between genotypes and metabolic profiles of common genetic diseases in newborns, and explore the feasibility of using protein function artificial intelligence analysis platform and tandem mass spectrometry metabolite data to accurately predict the pathogenicity of

ectopic sites of genetic metabolic lesions through protein function prediction and metabolic level analysis of high-frequency mutation sites of genes, that is, to solve the pathogenicity of mutations with unknown clinical significance. It will also expand the types of disease diagnosis of neonatal MS / MS technology.

This study will also establish a risk assessment model for neonatal genetic metabolic disease gene screening results through artificial intelligence methods. By identifying the pathogenicity of mutation sites, especially those with unclear clinical significance, it can quickly identify high-risk children and reduce false positive rates, thereby improving the accuracy and system efficiency of neonatal genetic screening.

2. Research objective

(1) Gene sequencing data (138 genes related to 133 common genetic diseases) and tandem mass spectrometry metabolomics data (11 amino acids and 28 acylcarnitines) of about 40,000 newborns from the South China Neonatal Genetic Screening Alliance participating units were collected and collated to complete the database construction of genes and mass spectrometry.

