model were established. Construction and selection of modeling indicators, select core indicators through information gain and correlation coefficient, and construct combined features ; in the model training stage, the gene screening data is divided into training set and test set at a ratio of 8 : 2, and the ensemble learning models such as random forest, gradient boosting tree algorithm and artificial neural network are trained to select the best model. Model evaluation, the model selection process first meets the detection rate of 1, and then compares the false positive rate to select the optimal training model. Model verification, using a new batch of big data samples, through model calculation, output high-risk and low-risk sample lists, and compare and analyze with the original screening results.

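### Outcome-based indicator selection is listed before the 8:2 split and is not confined to the training set; done in that order, test-set sensitivity looks too high and the false-positive rate too low

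*Combined protocol and SAP*

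**What the plan says.** Section 3.3, item (4) describes an artificial intelligence risk assessment model in stages.

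- It opens with correlation work on the full collection: "By analyzing the correlation between large sample gene data and tandem mass spectrometry data". No partition is mentioned.
- Indicators come next, and the text runs straight on into the following stage: "select core indicators through information gain and correlation coefficient, and construct combined features ; in the model training stage, the gene screening data".
- The split belongs to that following stage: "in the model training stage, the gene screening data is divided into training set and test set at a ratio of 8 : 2".
- Evaluation follows: "the model selection process first meets the detection rate of 1, and then compares the false positive rate to select the optimal training model". The data set used for this comparison is not named.
- Last comes verification on a new batch of samples, compared with the original screening results. Its source, size and period are not given.

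Section 3.7 lists accuracy, balanced accuracy, sensitivity and specificity without saying which records they are computed on. No section mentions cross-validation or limits indicator selection to training records.

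**The concern.** Information gain is computed against the outcome label. The correlation coefficient may be too, although the plan does not say what is correlated with what. If all records enter this step, the labels of the 20% help decide which indicators and combinations the model may use. The 20% is then no longer an independent test, even if every model weight is fitted on the 80% alone.

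The mechanism is simple. With a proportional split, the mean of a feature over all cases is 0.8 × (training-case mean) + 0.2 × (test-case mean). Ranking on the whole favours features whose chance deviation in the test cases agrees with that in the training cases. Such features then appear to be confirmed in the test set.

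At stake is the figure that picks the model. Detection is fixed at 1 first, so candidates are separated by their false-positive rates, and leakage makes those rates look better than they are. An indicator with no diagnostic value could be carried forward.

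**Working it through.** The plan states no expected detection or false-positive rate, so there is no figure to reproduce. The check sizes the effect by simulation under stated assumptions.

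**Inputs**

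- Records: "Gene screening and tandem mass spectrometry data of 40,000 newborns" (Abstract). If all are divided, 0.8 × 40,000 = 32,000 and 0.2 × 40,000 = 8,000.
- Candidate indicators: "tandem mass spectrometry metabolomics data (11 amino acids and 28 acylcarnitines" (section 2, objective 1), so 11 + 28 = 39 analytes. If combined features are two-analyte combinations, 39 × 38 / 2 = 741, for 780 features in all. That the core indicators are these analytes, and that combinations are pairwise, are assumptions.
- Positives per outcome: not given. Section 1.1 quotes positive rates of 2.3%, about 4.0% and 8.81% from three screening studies. Applied to 40,000 they give 920, 1,600 and 3,524 positives over all diseases. Spread evenly over 133 diseases, they give 920/133 ≈ 7, 1,600/133 ≈ 12 and 3,524/133 ≈ 26. The even spread is an assumption.

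**Method**

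For feature j, d_j = case mean − control mean. Keep the features with the largest |d_j|, computed either on all records or on the 80% only. In both arms the weights of a linear score are fitted on the 80%. On the 20%, read the AUC and the false-positive rate at detection 1, which is the share of controls scoring at least as high as the lowest-scoring case.

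**Result 1: no true signal, independent analytes, top 5 kept** (20,000 records and 60 runs for 10-160 cases; 40,000 records and 15 runs for 1,600)

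| Cases | AUC, all records | AUC, training only | False-positive rate, all records | False-positive rate, training only |
|---|---|---|---|---|
| 10 | 0.79 | 0.51 | 0.35 | 0.68 |
| 40 | 0.65 | 0.48 | 0.79 | 0.90 |
| 160 | 0.58 | 0.50 | 0.95 | 0.97 |
| 1,600 | 0.53 | 0.51 | 1.00 | 1.00 |

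Monte Carlo standard errors in this table are at most 0.027 for AUC and 0.032 for the false-positive rate.

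**Result 2: no true signal, top 10 kept**

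With correlated analytes, 4,000 controls and 200 runs, 7, 12 and 26 cases give AUC 0.86, 0.80 and 0.69 with selection on all records, against 0.51, 0.51 and 0.50 with training-only selection. Single analytes without combinations still give 0.75, 0.70 and 0.63. A rerun at larger counts, again with combinations and top 10, gives 0.63 against 0.50 (100 cases), 0.55 against 0.51 (400), 0.54 against 0.50 (920 and 1,600) and 0.53 against 0.51 (3,524).

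**Result 3: two analytes truly shifted by 1 SD, otherwise as Result 1**

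At 10, 40, 160 and 1,600 cases, AUC is 0.87, 0.82, 0.83 and 0.82 with all records, against 0.72, 0.76, 0.81 and 0.81. The false-positive rate at detection 1 is 0.20, 0.54, 0.71 and 0.94, against 0.40, 0.63, 0.76 and 0.94.

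In every setting the bias falls as cases increase. Where it is visible, it raises AUC and lowers the false-positive rate.

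**The case against.** Four arguments carry weight.

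1. *The plan is silent, not wrong.* Item (4) is a terse, translated list of topics and never says which records are used for selection. A reader might infer that the test set has in fact helped choose the indicators. The documents do not establish that; it is implied by the order of the steps. What stands is that the stated order permits it and no safeguard is written.

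2. *The link to the MS/MS disease models is not established.* Item (4) speaks of core indicators, divides gene screening data, and names random forest, gradient boosting and neural networks. Sections 3.6(6) and 3.7 name random forest, support vector machine, elastic net and multilayer perceptron, with no filter step and no 8:2 split. It is tempting to say that the aim of adding 2-3 MS/MS-diagnosable diseases rests on these test-set figures. The plan does not say so. The most that can be said is that those models are affected if they follow the same procedure.

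3. *Case counts may be large.* The plan targets common diseases, and the high-risk and low-risk lists it will output can be read as pooling all positives. With 920 or more positives the bias is small. This stands, so the low-count results should not be read as the expected size.

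4. *A new batch follows.* Truly independent records would be untouched by this leakage. That also stands, but the batch is undefined, and a later check cannot undo a choice of features and model already made on optimistic figures.

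A further inference, that the regional standardisation in item (3) leaks in the same way, is not supported. It is described as "In order to eliminate the influence of regional differences, the series detection index data were standardized", with no use of the outcome. Its effect was not simulated and is probably negligible with this many records.

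**Conclusion.** The point holds as a gap in specification with a predictable direction of bias. If item (4) is carried out in the order written, test-set sensitivity is overstated and the false-positive rate understated. A reader might expect leakage to inflate both rates; for the false-positive rate that is the wrong direction.

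The size cannot be fixed from the documents because positives per modelled outcome are not given. It runs from serious (null AUC about 0.8 with 10-12 cases) through moderate (0.63-0.65 with 40-100) to small (0.53-0.54 with 920 or more). These figures rest on the assumed 780 features, the top 5 or 10 kept and a linear score. AUC is a convenient scale here, not a measure the plan names. They show a range and are not an estimate for this study.

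The order should be corrected before modelling. Given the exploratory aim, the unknown case counts and the planned new batch, the gap does not by itself invalidate the plan.

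**What to change.** Rewrite item (4) so that the newborns are divided 8:2 first. Carry out indicator selection, construction of combined features, tuning and the choice between models within the 80% only, inside each resampling fold if resampling is used. This includes the comparison of detection and false-positive rates. Freeze the result, evaluate it once on the 20%, and then apply it unchanged to the new batch.

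State the source, size and period of the new batch, the number of positives per modelled outcome, and whether the MS/MS models of section 3.6(6) follow the same procedure.

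The cost is a reordered paragraph and slightly more code. Reported performance will probably be less favourable, most visibly for outcomes with few positives.
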